Future studies: Finally, CSF and plasma samples will be saved for future studies on the effects of the two diets on metabolism (e.g. hormones of metabolism, such as incretins, glucagon, etc.), proteomic and metabolomic studies.

2. Study Objectives

Hypotheses and Specific Aims

1. To assess the effects of the two diets on exosomal p-S312-IRS-1, p-panY-IRS-1, and their ratio (brain IR);
2. To assess the effects of the two diets on other exosomal protein and mRNA biomarkers of AD;
3. To assess the effects of the two diets on S_I and HOMA-IR (peripheral IR);
4. To assess the effects of the two diets on liking ratings for calorie-rich foods and associated fMRI activation versus non-appetitive foods;
5. To assess the effects of the two diets on Stroop-associated fMRI activation;
6. To assess the effects of the two diets on intrinsic functional connectivity of the (DMN) assessed by resting fMRI;
7. To assess the effects of the two diets on glutamate, GABA, glucose and lactate in prefrontal cortex and hippocampus;
8. To assess the effects of the two diets on memory and executive function;
9. To assess the effects of the two diets on mood, level of energy, difficulty concentrating, headaches, feeling cold, constipation, negative emotions (depression, anxiety, irritability), hunger and preoccupation with food, and quality of life; To assess the effects of the two diets on clinical Labs: lipid panel, uric acid;
10. To assess the effects of the two diets on plasma ketones, such as β-hydroxybutyrate and other metabolites;
11. To assess the effects of the two diets on plasma and CSF AD biomarkers, including A_β₁₋₄₂ and p₁₈₁Tau;
12. To assess the effects of the two diets on plasma and CSF neurotrophic factors, such as BDNF;
13. To assess the effects of the two diets on plasma and CSF reactive oxygen species, advanced glycation end-products and advanced oxidation protein products;
14. To assess the effects of the two diets on plasma and CSF pro-inflammatory cytokines, such as IL-6, IL-8, IL-12 and IL-23;
15. To assess the effects of the two diets on anthropometric measures (weight, waist circumference, sagittal diameter);
16. To assess the effects of the two diets on physical activity as measured by accelerometry;
17. To assess the effects of the two diets on expression pattern of genes in candidate pathways;
18. To assess the effects of the two diets on the global gene expression pattern in PBMCs;

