At the end of the Outcome visit, participants will be given an accelerometer to wear for 96 hours. They will be given instructions on how to wear the device and to mail it back to the unit via a pre-paid envelope. To ensure more accurate estimates of physical activity, participants will keep an activity log of when they sleep, exercise, or bathe.

4.d.6. Procedures

Medical history: A NIA licensed practitioner (Physician or Nurse Practitioner) will obtain standardized medical history including past medical history, current review of systems, medications and supplements, as well as family history of Alzheimer's disease and dementia.

Physical examination: Vital signs including body temperature, blood pressure, and heart rate will be obtained. A NIA licensed practitioner (Physician or Nurse Practitioner) will conduct screening head, eyes, ears, nose, and throat (HEENT), cardiovascular, respiratory, abdominal, neurological exams.

Anthropometric measurements: Height, weight, waist circumference, and sagittal diameter will be obtained with the subject in a hospital gown without shoes.

PANAS: Participants will report on Likert scales how they feel emotionally. The PANAS is a common index of emotional state.⁷¹

Symptoms Review Questionnaire: Participants will report on Likert scales their mood, level of energy, difficulty concentrating, headaches, feeling cold, constipation, negative emotions (depression, anxiety, irritability), hunger and preoccupation with food during constriction and non-constriction days for the week prior to the visit.

RAND SF-36 scale: This questionnaire gauges physical and psychosocial effects of the dietary interventions. It has been used as a quality of life assessment in our previous 5-2 CR study.⁴⁰

Screening blood tests: After a 12-hour fast, 28 mL of blood will be drawn for the following blood tests: complete metabolic panel, liver function tests, complete blood counts, PT, PTT, INR, fasting lipid panel, HbA1c, TSH, insulin, HIV, HBV, and HCV.

Screening urine toxicology screen: Urine will be collected during the screening visit for a standard toxicology screen.

Urine pregnancy test: A urine pregnancy test (only in women who are able to become pregnant) will be performed at screening and before MRI or fluoroscopic LP procedures at the Baseline and Outcome Visits.

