- Any adverse event occurs Grade 2 or greater and possibly related to the study.
- The participant develops any of the exclusion criteria.
- There is persistent non-compliance with study requirements (keeping follow-up visits).

Participants will be informed about new information from this or other studies that may affect their health, welfare, or willingness to stay in this study. Participants may decide to stop participating at any time. Any data or blood collected until that point in time will remain part of the study and are the property of the National Institute on Aging.

9. Outcome measures

All secondary outcome variables in this pilot study are exploratory.

9. a. Primary outcome measures

- Exosomal p-S312-IRS-1/p-panY-IRS-1 ratio

9. b. Secondary outcome measures

- Other exosomal protein and mRNA biomarkers of AD;
- S_I and HOMA-IR, indices of insulin resistance, derived from insulin and glucose values taken from a fasting blood draw;
- fMRI activation to appetitive food versus non-appetitive food stimuli;
- Resting state fMRI intrinsic functional connectivity of DMN;
- Behavioral performance and fMRI activation during a Color-Word Stroop task;
- Brain metabolites assessed with Magnetic Resonance spectroscopy and regional perfusion assessed with arterial spin labeling;
- Memory and executive function scores.
- Anthropometric measures (weight, waist circumference, sagittal diameter);

- Clinical Labs: lipid panel, uric acid;
- Plasma ketones, such as β -hydroxybutyrate and other metabolites.
- Plasma metabolites and hormones (GLP-1, insulin) during a mixed meal test;
- CSF and plasma AD biomarkers, including $\text{A}\beta_{1-42}$ and p_{181}Tau ;
- Plasma and CSF neurotrophic factors, such as BDNF;
- Plasma and CSF reactive oxygen species, advanced glycation end-products and advanced oxidation protein products;
- Plasma and CSF pro-inflammatory cytokines, such as IL-6, IL-8, IL-12 and IL-23;
- Ratings of symptoms that can occur with 5-2 CR, mood and quality of life changes, recorded during both the 5-2 CR and control diet phases;
- Physical activity measured using an accelerometer.
- Global gene expression pattern, mitochondria gene expression and expression of other gene pathways responding to CR
- Genome-wide methylation in peripheral blood mononuclear cells

10. Statistical Analysis

10. a. Analysis of data/study outcomes

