This is a pilot study that is exploratory in nature and one of its goals is to collect preliminary data for multiple outcomes that may be used in future studies on the brain effects of CR.

For the primary and each secondary scalar measure, a separate repeated measures mixed models analysis will be conducted to examine the effects of the between-subjects factor “Group” (5-2 CR group vs. “Healthy living” control group), the within-subjects factor “Time” (Baseline vs. Outcome) and their Interaction. An Auto-Regressive (AR)1 covariance matrix and Restricted Maximum Likelihood Estimation (REML) will be used. We will assess fit to the model using the AIC and BIC criteria (lower values indicate better fit). These parameters were chosen because they are recommended for repeated measures analyses, including fMRI task analyses.¹⁰⁰ Regarding within-subjects effects, we will assess post-hoc differences between the 8-week outcome visit and baseline for the 5-2 CR and control groups and for each group separately (i.e. post-hoc tests for the Group * Time interaction). This analytic approach is common in the CR literature.¹⁰¹ Mixed model post-hoc tests will employ the Least Significant Difference (LSD) statistic. We will use one-tailed t-tests.

Criteria for significance will be set at alpha of 0.05 for all non-MRI analyses, and 0.005 uncorrected at the voxel level for fMRI analyses. Given that this pilot study is exploratory, we will not conduct correction of multiple comparisons for the various secondary outcomes.

Analysis of fMRI data will use a mixed model design to assess the effect of Group on

brain activation associated with viewing appetitive vs. non-appetitive food, the Stroop effect in the Stroop task, and DMN intrinsic functional connectivity. Analyses will be conducted at the whole brain level and within ROIs (vmPFC, OFC and insula for the fMRI food task, lateral and dmPFC for the Stroop task, and in DMN for resting state. The fMRI analyses will be corrected for type 1 error as the cluster level using Monte Carlo simulations.

For brain MRS measures, a repeated measures analysis will be separately used for each of the brain regions of interest: the hippocampus and the prefrontal cortex.

APOE genotype is a common covariate used when assessing populations with AD or at risk for AD. We intend to perform exploratory analyses including APOE, which may reduce error variance and improve our statistical models.

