ATTACHMENT E. Symptoms Review Questionnaire for 5-2 CR participants

Symptoms Review Questionnaire

Intermittent Calorie Restriction

Since **last week**, on a 1-10 scale, please rate how you felt on **NON-CR DAYS** for:

	Less	→	More								
Amount of Energy	0	1	2	3	4	5	6	7	8	9	10
Ability to Concentrate	0	1	2	3	4	5	6	7	8	9	10
Constipation	0	1	2	3	4	5	6	7	8	9	10
Headache Severity (if any)	0	1	2	3	4	5	6	7	8	9	10
Feeling Cold	0	1	2	3	4	5	6	7	8	9	10
Feeling Sad/Depressed	0	1	2	3	4	5	6	7	8	9	10
Feeling Irritable	0	1	2	3	4	5	6	7	8	9	10
Feeling Anxious	0	1	2	3	4	5	6	7	8	9	10
Feeling Hungry	0	1	2	3	4	5	6	7	8	9	10
Preoccupation with Food	0	1	2	3	4	5	6	7	8	9	10

Since **last week**, on a scale from 1-10, please rate how you felt on **CR DAYS** for:

	Less	→	More								
Amount of Energy	0	1	2	3	4	5	6	7	8	9	10
Ability to Concentrate	0	1	2	3	4	5	6	7	8	9	10
Constipation	0	1	2	3	4	5	6	7	8	9	10
Headache Severity (if any)	0	1	2	3	4	5	6	7	8	9	10
Feeling Cold	0	1	2	3	4	5	6	7	8	9	10
Feeling Sad/Depressed	0	1	2	3	4	5	6	7	8	9	10
Feeling Irritable	0	1	2	3	4	5	6	7	8	9	10
Feeling Anxious	0	1	2	3	4	5	6	7	8	9	10
Feeling Hungry	0	1	2	3	4	5	6	7	8	9	10
Preoccupation with Food	0	1	2	3	4	5	6	7	8	9	10

Have you experienced any other symptoms that you did not have before going on the diet? If so, please write down those symptoms here:

Participant ID: _____

Investigator/Staff Name: _____

Date: _____

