ATTACHMENT E. Symptoms Review Questionnaire for “Healthy Living Diet” participants

Symptoms Review Questionnaire

Healthy Living Diet

Since **last week**, on a scale from 1-10, please rate these items for how you felt

	Less	→	More
Amount of Energy	0	1	2 3 4 5 6 7 8 9 10
Ability to Concentrate	0	1	2 3 4 5 6 7 8 9 10
Constipation	0	1	2 3 4 5 6 7 8 9 10
Headache Severity (if any)	0	1	2 3 4 5 6 7 8 9 10
Feeling Cold	0	1	2 3 4 5 6 7 8 9 10
Feeling Sad/Depressed	0	1	2 3 4 5 6 7 8 9 10
Feeling Irritable	0	1	2 3 4 5 6 7 8 9 10
Feeling Anxious	0	1	2 3 4 5 6 7 8 9 10
Feeling Hungry	0	1	2 3 4 5 6 7 8 9 10
Preoccupation with Food	0	1	2 3 4 5 6 7 8 9 10

Have you experienced any other symptoms that you did not have before going on the diet? If so, please write down those symptoms here:

Participant ID: _____

Investigator/Staff Name: _____

Date: _____

26. Consent forms

Please see attached consent forms for healthy adult volunteers.

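### The symptom questionnaire asks the two arms different questions, so no hunger or symptom score comparable across arms and visits is defined for the planned Group x Time model

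*Combined protocol and SAP*

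**What the plan says.** - **Objective.** Specific aim 9 in section 2 is "To assess the effects of the two diets on mood, level of energy, difficulty concentrating, headaches, feeling cold, constipation, negative emotions", together with hunger, food preoccupation and quality of life.
- **Outcome.** Section 9.b lists "Ratings of symptoms that can occur with 5-2 CR, mood and quality of life changes, recorded during both the 5-2 CR and control diet phases". It names no scoring rule and no day type.
- **Instrument.** Section 4.d.6 has participants rate symptoms, including "hunger and preoccupation with food during constriction and non-constriction days for the week prior to the visit", without limiting this to one arm.
- **Forms.** Attachment E has two. The 5-2 CR form uses the stem "please rate how you felt on" twice, once for non-CR days and once for CR days, with the same 10 items each time. The Healthy Living form has one block: "please rate these items for how you felt". The items and the 0-to-10 response columns are the same on both.
- **Schedule.** Table 1 places the questionnaire at Screening, Baseline and Outcome. Section 4.d.4 also has it completed at Compliance Visits, which Table 1 does not show. No form is named for Screening or Baseline.
- **Analysis.** Under section 10.a, for each secondary scalar measure "a separate repeated measures mixed models analysis will be conducted", with Group, Time (two levels, Baseline and Outcome) and their interaction.

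**The concern.** The model needs one value per participant at each of two visits, measured in the same way in both arms. At Outcome a 5-2 CR participant has two values per item, and neither answers the whole-week question put to controls. A control participant has no CR days to rate. At Baseline nobody has had a CR day, and the document does not say which page is handed out.

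At stake is the interpretation of the tolerability items. With nothing fixed in advance, the analyst can use the CR-day block, the non-CR block or some average of them, and can choose after seeing the data. Section 10.a applies no multiplicity correction to secondary outcomes, so nothing else limits that choice. A whole-week rating that was never collected in the 5-2 CR arm also cannot be recovered later.

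**Working it through.** The plan gives no effect size, SD or power figure for the symptom ratings, so there is no figure of its own to reproduce. The check compares the forms and then shows how far the answer depends on the block used.

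**Forms side by side**

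| | 5-2 CR form | Healthy Living form |
|---|---|---|
| Blocks | non-CR days; CR days | whole week |
| Ratings per administration | 10 x 2 = 20 | 10 |
| Asks the whole-week question | no | yes |
| Closing question | presumes the diet has begun | presumes the diet has begun |

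Because of its closing question, neither page fits Screening or Baseline as written. Section 4.d.3 randomizes after the Baseline procedures, and on that reading an arm-specific page could not be chosen at Baseline. Section 4.d.1 lists randomization before the Baseline Visit.

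**Dependence on the block**

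Let C and N be the 5-2 CR minus control differences in change on CR days and non-CR days. With two CR days in seven, the day-weighted weekly difference is

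W = (5N + 2C)/7, and C/W = 7C/(5N + 2C).

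When N = 0, C/W = 7/2 = 3.5. All values of C and N below are assumed.

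| C | N | CR-day block | Non-CR block | Day-weighted week W | Simple mean of blocks |
|---|---|---|---|---|---|
| 3 | 0 | 3.0 | 0 | 6/7 = 0.86 | 1.5 |
| 2 | 0 | 2.0 | 0 | 4/7 = 0.57 | 1.0 |
| 1 | 0 | 1.0 | 0 | 2/7 = 0.29 | 0.5 |
| 3 | 1 | 3.0 | 1 | 11/7 = 1.57 | 2.0 |
| 2 | -0.5 | 2.0 | -0.5 | 1.5/7 = 0.21 | 0.75 |

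In the fourth row the ratio is 3/1.57 = 1.9, so 3.5 holds only when N = 0.

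**What this does to a test**

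Inputs: 20 per arm (section 10.b); one-tailed alpha 0.05 (section 10.a); correlation between visits 0.4 (section 10.b, stated for the primary outcome and borrowed here); item SD 1.5 to 2.5 (assumed, and taken as the same for every score); C = 2 and N = 0 (assumed).

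SD of change = SD x sqrt(2 x (1 - 0.4)). SE of the group difference = SD of change x sqrt(2/20). Power by the normal approximation is Phi(difference/SE - 1.645).

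| Item SD | SE | CR-day block (2.0) | Day-weighted week (0.57) | Non-CR block (0) |
|---|---|---|---|---|
| 1.5 | 0.52 | 0.99 | 0.29 | 0.05 |
| 2.0 | 0.69 | 0.89 | 0.21 | 0.05 |
| 2.5 | 0.87 | 0.75 | 0.16 | 0.05 |

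The same participants and the same assumed symptoms give a likely positive finding, an unlikely one, or only the false-positive rate, according to the block used.

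**The case against.** **Aim 9 does not rest on this questionnaire alone.** PANAS and RAND SF-36 are given to everyone at Baseline and Outcome with no arm-specific version. The stated hypothesis in this area, in the cognition and affect part of the Introduction, concerns affect and quality of life. This stands, so a reader who infers that the whole objective is untestable goes too far. It does not rescue the remaining items. The Introduction reads as if those two instruments also cover hunger, cold, constipation and headache, but the PANAS in Attachment D contains none of these, and the RAND SF-36 is not reproduced. PANAS also asks about the present moment rather than the week. The weekly contacts in section 4.a.2 raise the symptoms without a day-type split, but no scoring is given for them.

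**A weekly score can be built from what is collected.** Items and response scale match, so a 5:2 weighted mean would give an approximate contrast. This also stands, but the plan does not specify it, and a weighted mean of two recalled ratings is not the same measurement as one whole-week recall.

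**The Baseline problem may be smaller than it looks.** Nothing says the 5-2 CR page is used at Baseline. Before the diet every day is a non-CR day, so a weekly value could be obtained. That is fair; the defect is that the form is not named.

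**Bias in a known direction is not established.** A reader might infer that the CR-day block must overstate symptoms and the non-CR block must understate them. That presumes CR days are worse. The Introduction says moderate CR typically leaves appetite unaffected, and section 7.p reports that some participants on this regimen had more energy (6%) or better mood and self-confidence (32%). A CR-day contrast is also a legitimate quantity of its own, provided it is declared as such.

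**The stakes are limited.** Section 9 declares all secondary outcomes exploratory. That is correct and caps the severity.

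**Conclusion.** The point holds in this form: the 5-2 CR arm is never asked the question put to controls, the Baseline form is unnamed, and no common score is defined, so the Group x Time contrast is unspecified for the questionnaire items. This is a gap in the data collected as well as in the analysis text. It bears chiefly on hunger, food preoccupation, cold, constipation, headache, energy and concentration. The sad, irritable and anxious items share the mismatch, but mood can be tested through PANAS and quality of life through RAND SF-36.

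The fork between blocks is certain; its size is not. The 7/2 ratio and the zero follow from arithmetic only if non-CR days equal control days, and the power ranges rest on assumed shifts and SDs. This is a worthwhile, inexpensive correction to an exploratory secondary outcome.

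**What to change.** - Give both arms the same whole-week 10-item page, neutrally titled, at Baseline, each Compliance Visit and Outcome. The existing control page serves, with the closing question about symptoms since starting the diet removed at Baseline.
- State in sections 4.d.6 and 10.a that this page supplies the value entered in the Group x Time model.
- Keep the CR-day/non-CR-day page for the 5-2 CR arm as a within-arm description only.
- Align Table 1 with section 4.d.4 on the Compliance Visits.
- If data are already collected, pre-specify (5 x non-CR + 2 x CR)/7 per item as the 5-2 CR value before analysis, state which form supplied the Baseline value, and label the contrast approximate.

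The cost is one extra short page per visit for 5-2 CR participants, a minute or two of their time, one sentence in each of the two sections and a table edit. One asymmetry remains. Compliance and Outcome Visits for the 5-2 CR arm fall on a restriction day, while controls attend on any convenient day, so whole-week recall may still be coloured by how 5-2 CR participants feel that day. The report should say so.
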